	Grade 2	Interrupt until after consulting an ophthalmologist. Topical corticosteroids, cycloplegic agents, systemic corticosteroids May resume ICPi treatment once off systemic corticosteroids, which are purely indicated for ocular adverse effects or once corticosteroids for other concurrent systemic irAEs are reduced to ≤ 10 mg; continued topical/ocular corticosteroids are permitted when resuming therapy to manage and minimize local toxicity. Re-treat after return to G1 or less
	Grade 3–4	Permanently discontinue. Emergent ophthalmology referral. Systemic

Drug-Related Toxicities	Severity	Management
		corticosteroids (IV prednisone 1-2 mg/kg or methylprednisolone 0.8-1.6 mg/kg) and intravitreal/periocular/topical corticosteroids per ophthalmologist opinion.
Episcleritis	Grade 1	Continue
	Grade 2	Interrupt and consult an ophthalmologist. Topical corticosteroids, cycloplegic agents, systemic corticosteroids
	Grade 3-4	Permanently discontinue. Urgent ophthalmology referral. Systemic corticosteroids and topical corticosteroids with cycloplegic agents
Blepharitis	No grades available	Continue, unless the symptoms are persistent and serious

SJS: Stevens-Johnson syndrome; TEN: toxic epidermal necrolysis; AGEP: acute generalized exanthematous pustulosis; DRESS: drug rash with eosinophilia and systemic symptoms; NSAIDs: Non-Steroidal Anti-Inflammatory Drug; DMARD: Disease-modifying antirheumatic drug; IVIG: Intravenous Immunoglobulin; CK: Creatine Kinase; PEX: Physical Examination; ATG: Antithymocyte Globulin; ICPi: Immune Checkpoint inhibitor.

Sintilimab treatment is allowed to be held for up to 12 weeks. If the symptoms do not resolve and treatment cannot be resumed within 12 weeks, the subject must permanently discontinue sintilimab treatment and enter the follow-up phase of the study except for the following two cases:

- Sintilimab hold > 12 weeks due to glucocorticoid taper while treating immune-related adverse events (irAEs): Consult the sponsor's medical monitor prior to resuming sintilimab. Tumor imaging evaluation for efficacy shall not be affected by treatment interruption and will be performed as scheduled.

- Sintilimab hold > 12 weeks due to AEs unrelated to sintilimab: Consult the sponsor's medical monitor prior to resuming sintilimab. Tumor imaging evaluation for efficacy shall not be affected by treatment interruption and will be performed as scheduled.

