5.2 Dose Adjustments

5.2.1 General principles

- The subject's hematologic, hepatic, and renal function must meet the requirements for study drug administration prior to Day 1 of each cycle. All the toxicities related to the

study drug must resolve to NCI CTCAE v5.0 grade 0 – 1 or baseline levels, excluding the following cases:

- Alopecia
- Grade 2 fatigue
- Hemoglobin (HGB) ≥ 8.0 g/dL
- Grade 2 neurotoxicities*
- Grade 2 weight loss
- All the dose adjustments should be documented, including the reasons and actions taken.
- The investigator should discuss with the sponsor to determine administration for any further concerns.

* refer to section 5.2.2 for more details

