5.2.2 Sintilimab dose adjustments

Dose adjustments for sintilimab are not permitted during the entire course of the study. Attached below is the reference table for sintilimab dose adjustments (only for sintilimab-related AEs determined by the investigator). If the administration delay occurs in a 3-week treatment cycle for sintilimab, all the subsequent administration should be delayed to ensure a dosing interval of 21 ± 3 days.

Sintilimab administration under special circumstances:

- An administration delay is not required for grade 3 lymphopenia.
- An administration delay is not required for any drug-related Grade 3 amylase or lipase abnormalities if it is not related to symptoms or clinical manifestations of pancreatitis.
- Administration can be continued for grade 3–4 drug-related endocrine AEs, such as adrenocortical insufficiency, hypophysitis, hyperthyroidism, hypothyroidism, and type I diabetes, that are adequately controlled with physiologic hormone replacement therapy (corticosteroids or thyroid hormone).

Table 4 Sintilimab dose adjustments

Drug-Related Toxicities	Severity	Management
1. Skin Toxicities		
Rash/Inflammatory Dermatitis	Grade 1	Continue, Consider topical emollients and/or mild-moderate potency topical corticosteroids
	Grade 2	Consider interruption, treat with topical emollients, oral antihistamines, and medium- to high-potency topical corticosteroids, Consider initiating prednisone 1 mg/kg, tapering over \geq 4 weeks
	Grade 3	Interrupt and consult a dermatologist to decide whether and when to resume the treatment, treat with topical emollients, oral antihistamines, and high-potency topical corticosteroids, Initiate (methyl)prednisolone or equivalent 1-2 mg/kg/d, tapering over \geq 4 weeks
	Grade 4	Interrupt and consult a dermatologist to decide whether and when to resume the treatment after resolving and prednisone requirement \leq 10 mg/day, Initiate (methyl)prednisolone or equivalent 1-2 mg/kg with slow tapering when toxicity resolves, initiate topical therapies recommended by a dermatologist
Bullous Dermatoses	Grade 1	Interrupt and consult a dermatologist to decide whether and when to resume the treatment

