	Grade 3–4	Continue, consult an endocrinologist, and symptom management
Hyperthyroidism	Grade 1	Continue and monitor closely
	Grade 2	Continue and monitor closely
	Grade 3–4	Continue, consult an endocrinologist, and symptom management
Primary Adrenocortical Insufficiency	Grade 1–2	Continue and monitor closely. For Grade 1, replacement therapy with prednisone (5-10 mg daily) or hydrocortisone (10-20 mg orally every morning, 5-10 mg orally in early afternoon). May require fludrocortisone (0.1 mg/d) for mineralocorticoid replacement in primary adrenal insufficiency. For Grade 2, initiate outpatient treatment at two to three times maintenance. (if prednisone, 20 mg daily; if hydrocortisone, 20-30 mg in the morning, and 10-20 mg in the afternoon) to manage acute symptoms. Taper stress-dose corticosteroids down to maintenance doses over 5-10 days Maintenance therapy as in G1.
	Grade 3–4	Continue, consult an endocrinologist, and symptom management. emergency department referral for normal saline (at least 2 L) and IV stress-dose corticosteroids on presentation (hydrocortisone 100 mg or

Drug-Related Toxicities	Severity	Management
		dexamethasone 4 mg. Taper stress-dose corticosteroids down to maintenance doses over 7-14 days after discharge. Maintenance therapy as in G1
Hypophysitis	Grade 1–2	Continue, monitor closely, and hormonal supplementation
	Grade 3–4	Continue, consult an endocrinologist, hormonal supplementation and initial pulse dose therapy with prednisone 1-2 mg/kg oral daily (or equivalent) tapered over at least 1-2 weeks
Diabetes	Grade 1	Continue and monitor closely
	Grade 2	Continue and monitor closely
	Grade 3–4	Continue and consult an endocrinologist to determine whether to resume the treatment
5. Musculoskeletal Toxicities		
Inflammatory Arthritis	Grade 1	Continue
	Grade 2	Interrupt until the symptoms are controlled and prednisone requirement is \leq 10 mg/day. If inadequately controlled by NSAIDS, initiate prednisone or prednisolone 10-20 mg/d or equivalent for 4-6 weeks. If improvement, slow taper according to response during the next 4-6 weeks; if no improvement after initial 4-6 weeks, treat as G3. If unable to lower corticosteroid dose to 10 mg/d after 3 months, consider DMARD Consider intra-articular corticosteroid injections for large joints
	Grade 3–4	Interrupt consult a rheumatologist to decide whether to resume the treatment after resolving to grade 0–1. Initiate oral prednisone 0.5-1

Drug-Related Toxicities	Severity	Management

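### For Grade 3-4 drug-related endocrine events not yet controlled when a dose is due, 5.2.1, the 5.2.2 bullet and Table 4 do not give the same answer, and no text says which governs

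*Combined protocol and SAP*

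**What the plan says.** Section 5.2.1 sets the default before Day 1 of each cycle. Toxicities related to the "study drug must resolve to NCI CTCAE v5.0 grade 0 – 1 or baseline levels". Five exceptions follow: alopecia, Grade 2 fatigue, hemoglobin of at least 8.0 g/dL, Grade 2 neurotoxicity and Grade 2 weight loss. No endocrine event is among them.

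Section 5.2.2, under special circumstances, then has a bullet on endocrine events: "Administration can be continued for grade 3–4 drug-related endocrine AEs, such as adrenocortical insufficiency, hypophysitis, hyperthyroidism, hypothyroidism, and type I diabetes". It is qualified to events "that are adequately controlled with physiologic hormone replacement therapy (corticosteroids or thyroid hormone".

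The same section introduces Table 4 with "Attached below is the reference table for sintilimab dose adjustments". Its endocrine block covers the same five conditions. At Grade 3-4:

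- Primary hypothyroidism and hyperthyroidism (same wording in both rows): "Continue, consult an endocrinologist, and symptom management".
- Primary adrenocortical insufficiency: "Continue, consult an endocrinologist, and symptom management. emergency department referral for normal saline (at least 2 L) and IV stress-dose corticosteroids", with the taper to maintenance running over 7-14 days after discharge.
- Hypophysitis: "Continue, consult an endocrinologist, hormonal supplementation and initial pulse dose therapy with prednisone 1-2 mg/kg oral daily", tapered over at least 1-2 weeks.
- Diabetes: "Continue and consult an endocrinologist to determine whether to resume the treatment".

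Section 5.3 sends the reader to Table 4 for dose adjustment, and Section 8.6.1 sends the reader to Section 5.2 as a whole. No sentence ranks the text against the table.

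**The concern.** The bullet attaches a condition to continued dosing, and the table rows for the same events do not. In two of those rows the instruction to continue stands beside steroid treatment that, by the table's own figures, exceeds replacement. A subject may reach a dosing day with such an event unresolved and not yet controlled. The protocol then does not settle whether that dose is permitted.

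What is at stake is first the handling of a severe or life-threatening event. Second is the record. Section 4.4.1 ties mandatory discontinuation for adverse events to Section 5.2, Section 9.3.3 reports subjects who violate the regimen, and Section 9.2 removes subjects with major violations that affect efficacy evaluation from the per-protocol set. If the governing text is unclear, so is whether a given dose was a violation.

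**Working it through.** No calculated figure of the plan is involved, so the check is a comparison of texts, followed by a rough count.

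**Row count.** Of the five Grade 3-4 endocrine rows in Table 4, 5 of 5 open with an instruction to continue, 0 of 5 carry the bullet's condition, and 2 of 5 (hypophysitis and adrenal) pair continuation with pulse-dose or stress-dose steroids.

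**By state of the event on the dosing day.**

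| Event when the dose is due | 5.2.1 | 5.2.2 bullet | Table 4 |
|---|---|---|---|
| Back to grade 0-1 or baseline | Requirement met | Not needed | Grade 3-4 row no longer applies |
| Grade 3-4, controlled on replacement | Not met, unless the bullet is read as an exception | Dosing can continue | Continue |
| Grade 3-4, not yet controlled | Not met | Allowance does not reach it | Continue |

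The first line causes no difficulty. In the second, the bullet and table agree, and 5.2.1 fits if the bullet is its exception. Only the third leaves a conflict. The diabetes row is set aside here because it does not read consistently on its own.

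**Are the steroid doses replacement doses by the table's own figures?** The Grade 1 adrenal row gives replacement as prednisone 5-10 mg daily. The Grade 3-4 hypophysitis row gives 1-2 mg/kg. The documents give no body weight. At an assumed 70 kg this is 70-140 mg, or 70/10 = 7 to 140/5 = 28 times the replacement figure. At an assumed 50-90 kg the range is 50/10 = 5 to 180/5 = 36 times. The replacement figure is borrowed from another row, so the ratio only shows that the two are of different size. In the adrenal row, the taper down to maintenance shows that the stress dose lies above it.

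**Can that treatment meet a dosing day?** The dosing interval is 21 ± 3 days. A taper of 7-14 days may or may not include an infusion day, depending on when the event began. Overlap is possible but not certain.

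**Does the table normally state such conditions?** Yes. Grade 2 inflammatory arthritis is interrupted until symptoms are controlled and prednisone is at most 10 mg/day. Grade 2 hepatitis resumes at grade 0-1 with the same steroid limit. The endocrine rows' silence is therefore hard to treat as mere abbreviation.

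**Diabetes.** The row tells the investigator to continue and also asks whether to resume, which presupposes a hold. The bullet names type I diabetes, but its parenthesis lists only corticosteroids or thyroid hormone, so it does not say how control of diabetes is to be judged.

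**Expected number.** Section 1.2.2 reports Grade 3 or higher treatment-related events in 111 of 595 Chinese subjects. Those it names at 1% or more are decreased platelets (1.2%), neutrophils (1.0%) and lymphocytes (1.0%). If that list is complete, each endocrine term is below 1%, which gives fewer than 25 × 0.01 = 0.25 expected subjects per term. Even if all five terms sat just under 1%, the sum would be below 5 × 0.25 = 1.25.

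**The case against.** The best reply is that the texts form a workable hierarchy: 5.2.1 is the default, the bullet is the exception, and Table 4 is a reference table introduced by that text and meant to be read with it. The Grade 3 lymphopenia bullet does match its table row. All five Grade 3-4 endocrine rows call for an endocrinologist, and 5.2.1 tells the investigator to take further concerns to the sponsor. This reading is reasonable, but the protocol does not state it, and the rows as printed do not point back to the bullet.

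Several stronger readings are tempting and are not supported:

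- *That the bullet allows dosing only if the event is controlled.* It says dosing can be continued for controlled events. The limit comes from reading it with 5.2.1.
- *That the bullet and the table give opposite orders.* Neither the bullet nor any of the five rows says to hold. The hold follows only from 5.2.1.
- *That Table 4 directs infusion during emergency or pulse-dose treatment.* Continuing on a three-week schedule need not mean that.
- *That the 14.1% hypothyroidism rate in Section 1.2.2 measures the problem.* That rate is for any grade.
- *That practice will vary between sites.* Section 8.4.1 describes a single-site protocol, so any variation lies in the investigator's reading.
- *That the diabetes row is further proof of the conflict.* It is a separate wording error.

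**Conclusion.** The inconsistency is real and narrow. It concerns a Grade 3-4 drug-related endocrine event that is not yet controlled when a dose is due. There, 5.2.1 is not satisfied, the bullet's allowance does not apply, and the table says to continue. The diabetes row needs correction in its own right.

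The conclusion rests on reading the bullet as a limited exception to 5.2.1. That is an inference, but without it the bullet's qualifier would have no function.

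The numerical effect is small. The figure of under 0.25 subjects per term assumes that the list in Section 1.2.2 is complete and that its rates carry over. It comes from the Chinese cohort; the section gives no Grade 3 or higher breakdown for the 36 US subjects. Median treatment at 200 mg every three weeks was 24.29 weeks, against a maximum of 24 months here. A material effect on exposure, discontinuation or deviation counts is not shown, and nothing here bears on the two-stage response design. The point should be fixed because it touches patient safety and leaves compliance undefined in the few cases where it arises.

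**What to change.** At the next amendment:

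1. Reconcile 5.2.1, the endocrine bullet in 5.2.2 and the five Grade 3-4 endocrine rows of Table 4, so that the same condition for dosing appears in each.
2. Correct the diabetes row so that it no longer both continues and asks about resuming, and make the bullet's treatment of type I diabetes consistent with its list of replacement therapies.
3. State which text governs if the general principles, the bullets and the table differ.

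The clinical team must choose the rule; none is proposed here. The cost is protocol wording, with no change to sample size, analysis or data collection.

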5.2.3 Management of sintilimab-related infusion reactions

Sintilimab may cause severe or life-threatening infusion reactions, including severe hypersensitivity reactions or allergic reactions. Signs and symptoms usually occur during or after drug infusion and usually resolve within 24 h after the infusion completion. Refer to [Table](#) for the guidelines for management of sintilimab-related infusion reactions.

Table 5 Guidelines for the management of sintilimab-related infusion reactions

NCI CTCAE Grades	Treatments	Premedications for Subsequent Infusions
Grade 1 Mild reaction; infusion interruption not indicated; intervention not indicated	Monitor the subject, including vital signs, closely until the subject is stable as determined by the investigator.	Not applicable.
Grade 2 Treatment or infusion interruption required, but responds promptly to timely symptomatic treatment (e.g. antihistamines, nonsteroidal anti-inflammatory drugs [NSAIDS], anesthetics, IV fluids); prophylactic medications indicated for ≤ 24 h	Stop the infusion and monitor symptoms. Other appropriate treatments include but are not limited to: IV fluids Antihistamines NSAIDS Acetaminophen Consider bronchodilators Consider corticosteroids Monitor the subject, including vital signs, closely until the subject is stable as determined by the investigator. If symptoms resolve within 1 h after interrupting the infusion, then the infusion will be resumed at 50% of the original infusion rate (e.g. from 100 mL/h to 50 mL/h).	Premedications should be given for subsequent infusions. The following premedications are recommended within 1.5 h (± 30 min) prior to sintilimab infusion: Diphenhydramine 50 mg PO (or equivalent antihistamines) Acetaminophen 500–1000 mg PO (or equivalent antipyretics) If grade 2 toxicities occur despite of adequate premedications, the study drugs should be permanently discontinued.

NCI CTCAE Grades	Treatments	Premedications for Subsequent Infusions
	
If symptoms recur with resumption of the infusion, discontinue further treatment at that visit. Monitor the subject closely until the subject is stable.
 
If symptoms resolve in > 1 h, discontinue the treatment at that visit.
	
Grade 3 or 4 Grade 3 Prolonged (i.e. not rapidly responsive to symptomatic medication and/or brief interruption of infusion); recurrence of symptoms following initial improvement; hospitalization indicated for other clinical sequelae (e.g. renal impairment, pulmonary infiltration) Grade 4 Life threatening; pressors or ventilatory support indicated	
Discontinue the infusion.
 
Other appropriate treatments include but are not limited to:
 
Epinephrine**IV fluidsAntihistaminesNSAIDSAcetaminophenOxygenBronchodilatorsPressorsCorticosteroids 
Monitor the subject, including the vital signs, closely until the subject is stable as determined by the investigator.
 
Hospitalization may be indicated.
 
**Epinephrine should be used immediately for allergic reactions.
	
Not applicable.
 
The study drugs should be permanently discontinued.

Appropriate first-aid equipment should be provided in the ward and physicians should be available at all times during the administration.		
For more information, refer to CTCAE v5.0 (http://ctep.cancer.gov).		

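### Table 5 gives two opposite actions for an infusion reaction that recurs when the infusion is resumed: stop for that visit only (Grade 2 row) or stop for good (Grade 3 row)

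*Combined protocol and SAP*

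**What the plan says.** Table 5 in Section 5.2.3 has a column of grade definitions (headed as NCI CTCAE grades), a column of treatments and a column on premedication for later infusions.

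**Grade 2 row.** The definition is "Treatment or infusion interruption required, but responds promptly to timely symptomatic treatment". After the infusion is stopped there are three branches:

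- Early resolution: "If symptoms resolve within 1 h after interrupting the infusion, then the infusion will be resumed at 50% of the original infusion rate".
- Recurrence on restart: "If symptoms recur with resumption of the infusion, discontinue further treatment at that visit".
- Slow resolution: "If symptoms resolve in > 1 h, discontinue the treatment at that visit".

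The third column expects treatment to go on at later visits: "Premedications should be given for subsequent infusions". The only route to a permanent stop in this row is a Grade 2 reaction that occurs despite adequate premedication.

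**Grade 3 or 4 row.** Grade 3 covers a prolonged reaction, explained as "not rapidly responsive to symptomatic medication and/or brief interruption of infusion". It then lists further criteria: "recurrence of symptoms following initial improvement; hospitalization indicated for other clinical sequelae". The third column says: "The study drugs should be permanently discontinued".

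Section 4.4.1 lists, among the events after which a subject must stop treatment, an adverse event for which Section 5.2 requires it. Table 5 lies within Section 5.2. Sections 7.2 and 8.2 require adverse events to be graded by CTCAE v5.0.

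**The concern.** A subject whose symptoms settle, who restarts at half rate and whose symptoms then return is described by the Grade 2 treatment column and also by the Grade 3 definition. The first ends dosing for the day and leaves later premedicated infusions open. The second ends dosing altogether. Two investigators who both follow the table could therefore reach opposite decisions on re-exposure to a drug that Section 5.2.3 itself says may cause severe or life-threatening infusion reactions.

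The choice also reaches the results. Section 9.3.2.2 summarises and lists events leading to treatment discontinuation. Whether such a subject is counted there depends on which row was followed. In a study of 25, each such subject is visible in the rate.

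**Working it through.** The table states no figure to reproduce, so the check sets the branches of the Grade 2 row against the Grade 3 definition.

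**Recurrence on restart**

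1. The Grade 2 row permits restart only if symptoms resolved within 1 h of interrupting the infusion.
2. So every subject who restarts has already improved.
3. So every recurrence on restart is a return of symptoms after an initial improvement.
4. The Grade 3 definition lists exactly that as a criterion of its own, set apart by a semicolon from the prolonged-reaction criterion. No further condition has to be met.
5. The actions differ: stop for the visit, with premedication before later infusions, against a permanent stop.

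The match is one of meaning. The two rows use different words.

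**Where the conflict applies.** If the infusion was already premedicated because of an earlier reaction, the Grade 2 row itself leads to a permanent stop, and both rows agree. The conflict therefore concerns a reaction at an infusion given without such premedication, typically the subject's first reaction.

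**Resolution in more than 1 h**

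1. The Grade 2 branch has no upper time limit, so it can take in reactions that the Grade 3 row would call prolonged.
2. It also sits awkwardly with the Grade 2 definition, which requires a prompt response.
3. But the table gives no hour value for *promptly*, *rapidly* or *prolonged*. In addition, the grade definitions turn on response to treatment or interruption, while the 1 h test concerns resolution. A reaction may respond quickly and still take a little over an hour to clear.
4. So the overlap is possible and partial, and its starting point cannot be fixed from the table.

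**Size per subject.** With 25 subjects, 1/25 = 4 percentage points in the rate of discontinuation for an adverse event. If the 27 enrolled patients allowed for in 9.3.1.2 were all treated, it would be 1/27 = 3.7 points.

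**The case against.** **Stopping at that visit may be only the immediate step.** On this reading the investigator halts the infusion, re-grades the event to 3 and then follows the Grade 3 row. This is the best defence and would remove the conflict. But the table does not say it, and the Grade 2 row gives its own instruction for recurrence next to a column that foresees more infusions. The provision in 5.2.1 for discussing further concerns about administration with the sponsor is a fallback and does not settle which row governs.

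**The closing pointer to CTCAE v5.0, or the premedication rule, may settle it.** The pointer is general and names no row. The premedication rule deals with a reaction at a later, premedicated infusion and not with recurrence at the first event.

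**Stronger readings that the documents do not support**

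- A reader might infer that two of the three Grade 2 branches meet the Grade 3 definition. Only the recurrence branch clearly does.
- A reader might infer that the event carries two reportable grades. The treatment column assigns no grade, and CTCAE v5.0 governs grading under 7.2 and 8.2. On the table's own definition a recurrence can be graded 3. What is unresolved is the action.
- A reader might put a probability on the problem. The chance of at least one case in 25 is 1 − (1 − p)^25. For an assumed p of 1% to 5% this is 22% to 72%, and for an assumed 0.1% to 0.5% it is 2% to 12%. Nothing in the documents chooses between these. Section 1.2.2 lists the most common treatment-related events of grade 3 or above with incidence of at least 1% in 595 Chinese subjects, and infusion reactions are not among them. If that list is complete, such reactions were below 1% there. But events graded 2 would not appear, and no such list is given for the 36 US subjects.
- A reader might infer harm to the 12-week response endpoint. Subjects who stop for reasons other than radiographic progression continue tumor evaluation under 7.1.2. No passage makes them non-responders, and no effect on the two-stage design can be calculated.

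**Conclusion.** The point holds for recurrence on restart: Table 5 prescribes two incompatible actions for one event and gives no rule of precedence. This follows from the table's own logic and needs no outside source or assumed rate. It matters because Section 4.4.1 makes discontinuations required by Section 5.2 mandatory, and here that rule cannot be applied consistently.

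The consequences are the decision on re-exposure and a shift of about 4 points per affected subject in the discontinuation summary. How many subjects would be affected is unknown. The branch for resolution in more than 1 h is an undefined boundary and not a demonstrated contradiction. The primary analysis is not shown to be affected. This is a correction that should be made because it concerns a safety rule and is cheap to fix.

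**What to change.** The sponsor's clinicians should:

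1. Reconcile the Grade 2 and Grade 3 rows of Table 5 so that a reaction recurring on resumption leads to one action.
2. State how a reaction that takes more than 1 h to resolve relates to the Grade 3 definition.
3. Show the grade and the action separately, keeping the grade consistent with CTCAE v5.0 as required in 7.2 and 8.2, so that the severity and discontinuation summaries in 9.3.2.2 follow from one rule.

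Which action is right is a clinical decision, and no view on it is offered here. The cost is a wording change to one table, with no extra visits, data or patients.
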